QTcF	QT interval corrected for heart rate using Fridericia's formula

$R(AUC_{24h})$	accumulation ratio of multiple dose to first dose at regular administration for AUC_{24h}
$R(C_{max})$	accumulation ratio of multiple dose to first dose at regular administration for C_{max}
$R(C_{trough})$	accumulation ratio of multiple dose to first dose at regular administration for C_{trough}
$t_{1/2,z}$	terminal-phase elimination half-life
Treatment-emergent AEs (TEAEs)	treatment-emergent adverse event
t_{last}	time of last measurable (positive) concentration
t_{max}	time to maximum (peak) concentration

1 Introduction

This statistical analysis plan documents the details of the statistical analysis methodology to be applied in the protocol of Trial 351-102-00004.

2 Trial Objectives

Table 2-1 Trial Objectives and Endpoints	
Objectives	Endpoints
Primary Objective: To investigate the dose response in respect of weight decrease following repeated oral administration of OPC-131461 at 1, 2, 5, 10 mg or placebo in patients with CHF with volume overload despite having diuretics other than vasopressin antagonists.	Primary Efficacy Endpoint: Change in body weight from baseline to the last assessment time point (the day after investigational medicinal product [IMP] administration) by Day 8 Secondary Efficacy Endpoints: Change in body weight from baseline to the last assessment time point (the day after IMP administration) by Day 15 Percent change in body weight from baseline to the last assessment time point (the day after IMP administration) by Day 8 Percent change in body weight from baseline to the last assessment time point (the day after IMP administration) by Day 15 Improvement of or change in congestive findings (lower limb edema, pulmonary congestion, jugular venous distention, hepatomegaly, cardiothoracic ratio, pulmonary rales, and cardiac third sound) from the baseline to the last assessment time point (the day of IMP administration) by Day 7 Improvement of or change in congestive findings (lower limb edema, pulmonary congestion, jugular venous distention, hepatomegaly, cardiothoracic ratio, pulmonary rales, and cardiac third sound) from baseline to the last assessment (the day after IMP administration) by Day 15 Congestive findings (lower limb edema, pulmonary congestion, jugular venous distention, hepatomegaly, cardiothoracic ratio, pulmonary rales, and cardiac third sound), time to resolution of congestive findings, and the New York Heart Association (NYHA) Functional Classification

Table 2-1 Trial Objectives and Endpoints	
Objectives	Endpoints

Secondary Objectives:
 
To confirm the safety, tolerability, pharmacokinetics (PK) and pharmacodynamic of OPC-131461 versus placebo in patients with CHF with volume overload despite having received diuretics other than vasopressin antagonists.
	
Safety:
 
Adverse events (AEs), clinical laboratory test values, physical findings, vital signs, 12-lead electrocardiogram (ECG)
 
Pharmacodynamic Endpoints:
 
Serum osmolality, serum electrolyte (sodium, potassium) concentration, serum troponin I concentration, serum NT-proBNP concentration, serum creatinine concentration, serum cystatin C concentration, estimated glomerular filtration rate (estimated glomerular filtration rate using creatinine [eGFRcre], estimated glomerular filtration rate using cystatin C [eGFRcys]), plasma arginine vasopressin (AVP) concentration, plasma brain natriuretic peptide (BNP) concentration, plasma renin activity, and plasma aldosterone concentration
 
Daily urine volume/fluid intake/fluid balance
 
Urine volume/fluid intake/fluid balance in a time point set
 
Urine volume/fluid intake/fluid balance per hour
 
Urine osmolality, urine sodium excretion, urine potassium excretion, urine aquaporin 2 concentration, and free water clearance
 
Pharmacokinetic Endpoint:
 
Plasma concentrations and PK parameters of OPC-131461 and its metabolites

Exploratory Objective:
 
To conduct an exploratory investigation of OPC-131461 compared to placebo.
	
Exploratory Endpoint:
 
[REDACTED]
 
[REDACTED]
 
[REDACTED]

3 Trial Design

3.1 Type/Design of Trial

In this multicenter, randomized, double-blind, placebo-controlled, parallel-group, dose-ranging trial, 155 patients with CHF with volume overload despite having received diuretics other than vasopressin antagonists., will be randomized to receive OPC-131461 1 mg, 2 mg, 5 mg or 10 mg, or placebo (31 subjects/group) to investigate the dose response of OPC-131461 in respect of change in body weight from baseline at completion of 14-days of repeated oral administration.

The trial comprises the screening period, run-in period, treatment period, post-treatment observation period, and follow-up period. Subjects must be hospitalized from the day before the run-in period through the end of post-treatment examination. Once the post-treatment examination is finished, outpatient visits will be permitted.

After obtaining written informed consent from patients, the investigator or subinvestigator will perform the screening examination, determine eligibility of patients, and enroll eligible patients in the trial. Day 1 is defined as the day when the first dose of IMP is administered. The dose and regimen of any concomitant diuretics must remain unchanged from Day -3 in the run-in period through the end of the post-treatment examination. The use of diuretics, changes in body weight, and presence or absence of congestive findings during the run-in period will be assessed, and only subjects who meet the inclusion criteria for proceeding to the treatment period will be randomized to one of the treatment groups and then proceed to the treatment period.

The investigator or subinvestigator will allocate the IMP to subjects in a double-blinded fashion using the interactive web response system (IWRS) and then administer the IMP to them. Each subject will receive one of the following combinations in accordance with his or her assigned treatment group: only OPC-131461 tablets (1-mg or 5-mg tablets), OPC-131461 tablet (1-mg or 5-mg tablets) plus placebo tablet, or only placebo tablets.

During the treatment period, subjects will orally receive the IMP once daily for 14 days. However, the treatment will be terminated before completing 14 days of treatment, if the investigator or subinvestigator judges that no further improvement of volume overload is necessary in a case that all congestive findings present at baseline are resolved or in other cases. Subjects who complete the trial or who discontinue the trial after receiving the IMP will undergo the end-of-treatment (EOT) examination on the day after the final IMP administration, post-treatment examination 2 days after the final IMP administration, and follow-up examination 10 to 14 days after the final IMP administration. Subjects will also be followed up for AEs, as necessary.

All subjects should undergo EOT/withdrawal examination, post-treatment observation, and follow-up after the final IMP administration even if the actual treatment duration is less than 14 days as specified in the protocol.

The trial duration for each subject is from informed consent to the end of the follow-up examination.

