3.2 Trial Treatments

- Dosage regimen: Oral administration once daily

- Dose: OPC-131461 at 1 mg/day, 2 mg/day, 5 mg/day, 10 mg/day, or 0 mg
- Treatment duration: 14 days (However, the treatment will be terminated before completing 14 days of treatment, if the investigator or subinvestigator judges that no further improvement of volume overload is necessary in a case that any of congestive findings [lower limb edema, pulmonary congestion, jugular venous distension, hepatomegaly, pulmonary rales, and cardiac third sound] were resolved or in other cases.)

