8.3.2 Lower Limb Edema, Pulmonary Congestion

For lower limb edema and pulmonary congestion, improvement rates (percentages of subjects who have symptoms at baseline and show markedly improved or improved after IMP administration [improvement grading is as per Table 8.3-1]) and resolution rates (percentages of subjects who have symptoms at baseline and no symptoms after IMP administration) at the last assessment time point (the day of IMP administration) by Day 7 and the last assessment time point (the day after IMP administration) by Day 15, and their two-sided 95% CIs (Clopper-Pearson) will be determined for each group.

Fisher's exact test will be used to compare each OPC-131461 dose group and the placebo group.

For time to improvement and time to resolution ("time to improvement/resolution or censoring" minus "starting point", the same applies hereinafter), Kaplan-Meier plots will be prepared by treatment group for subjects with symptoms at baseline to estimate the median and the two-sided 95% CI (log-log transformation). Day -1 will be used as the starting point, and if no events have occurred as of the day after the final IMP administration of the study drug, the study will be censored at that point.

For changes in the severity of symptoms, shift tables from baseline to the last assessment on Day 7 (day of IMP administration), the last assessment on Day 15 (the day after IMP administration) and each time point after IMP administration will be prepared for each treatment group.

The improvement rate at each time point after administration of the IMP will be calculated for each treatment group.

Table 8.3-1 Improvement Grading for Lower Limb Edema and Pulmonary Congestion		
	Improvement Grading	Criteria for Assessment
1	Markedly improved	Symptom resolution or improvement by at least 2 grades
2	Improved	Improvement by 1 grade (symptom resolution will be assessed as markedly improved)
3	Unchanged	No change in the severity of symptoms/no symptoms throughout the trial period
4	Worsened	Worsening by at least 1 grade

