8.3.3 Pulmonary Rales, Cardiac Third Sound

For pulmonary rales and cardiac third sound, resolution rates (percentages of subjects who have symptoms at baseline and no symptoms after IMP administration) at the last assessment time point (the day of IMP administration) by Day 7 and the last assessment time point (the day after IMP administration) by Day 15, and their two-sided 95% CIs (Clopper-Pearson) will be determined for each group. Fisher's exact test will be used to compare each OPC-131461 dose group and the placebo group.

For the time to resolution, a Kaplan-Meier plot will be prepared for each treatment group in subjects with symptoms at baseline to estimate the median and two-sided 95% CI (log-log transformation). Day -1 will be used as the starting point, and if no events have occurred as of the day after the final IMP administration of the study drug, the study will be censored at that point.

For changes in the presence or absence of symptoms, shift tables from baseline to the last assessment on Day 7 (day of IMP administration), the last assessment on Day 15 (the day after IMP administration) and each time point after IMP administration will be prepared for each treatment group.

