8.3.4 Jugular Venous Distention, Hepatomegaly, Cardiothoracic Ratio

For changes in jugular venous distension, hepatomegaly, and cardiothoracic ratio from baseline, an analysis of covariance will be performed using treatment group as a fixed effect and baseline value as a covariate, and the differences in the least squares means between each OPC-131461 dose group and the placebo group at the last assessment time point (the day of IMP administration) by Day 7 and the last assessment time point (the day after IMP administration) by Day 15, and the two-sided 95% CIs (t-distribution) will be determined. Similar analysis will be performed using a model excluding baseline values.

For the last assessment by Day 7 (the day of IMP administration), the last assessment by Day 15 (the day after IMP administration), and each time point, descriptive statistics of the actual values and amount of change from the baseline will be calculated for each treatment group. For changes in the presence or absence of jugular venous distention and hepatomegaly, shift tables from baseline to the last assessment on Day 7 (day of IMP administration), the last assessment on Day 15 (the day after IMP administration) and each time point after IMP administration will be prepared for each treatment group.

For the time to resolution of jugular venous distention and hepatomegaly, a Kaplan-Meier plot will be prepared for each treatment group in subjects with symptoms at baseline to estimate the median and two-sided 95% CI (log-log transformation). Day -1 will be used as the starting point, and if no events have occurred as of the day after the final IMP administration of the study drug, the study will be censored at that point.

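### Does the difference between all and any resolved findings, in SAP Sections 3.1 and 3.2, leave the resolution analyses undefined or biased?

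*SAP*

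**What the plan says.** Section 3.1 allows treatment to end before 14 days if the investigator sees no need for further improvement of volume overload, "in a case that all congestive findings present at baseline are resolved or in other cases". Section 3.2 gives the same rule and the same judgement (the investigator "judges that no further improvement of volume overload is necessary"), but writes "in a case that any of congestive findings", lists six findings, and also ends by allowing other cases.

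The same six findings are secondary endpoints. For lower limb edema and pulmonary congestion (8.3.2) and for pulmonary rales and third sound (8.3.3), the resolution rate is defined as "percentages of subjects who have symptoms at baseline and no symptoms after IMP administration". It is taken at the last assessment by Day 7 and at "the last assessment time point (the day after IMP administration) by Day 15", and each dose is compared with placebo by Fisher's exact test.

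Time to resolution is estimated by Kaplan-Meier for those four findings and, in 8.3.4, for the other two: "For the time to resolution of jugular venous distention and hepatomegaly, a Kaplan-Meier plot will be prepared for each treatment group". The censoring rule is the same in all three sections. In 8.3.2 the condition and its consequence read: "no events have occurred as of the day after the final IMP administration of the study drug, the study will be censored at that point".

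**The concern.** The sentences in 3.1 and 3.2 are otherwise nearly the same, so the change from *all* to *any* reads as two different rules. Under *all*, a subject stopped for that circumstance has no baseline finding left. Under *any*, a subject could be stopped because one finding cleared while another persisted.

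The persisting finding would then be counted with those still present after a full 14 days. If the drug clears findings faster, more active subjects might be stopped in this way. The crude Day 15 resolution rate would then understate the contrast with placebo, and censoring at the last dose would depend on improvement in a related finding. No planned summary table cross-classifies early completers by the findings they still had.

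**Working it through.** **1. The two circumstances side by side.**

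| | Section 3.1 | Section 3.2 |
|---|---|---|
| Who decides | investigator or subinvestigator | investigator or subinvestigator |
| Judgement required | no further improvement necessary | no further improvement necessary |
| Named circumstance | all baseline findings resolved | any of six findings resolved |
| Other cases allowed | yes | yes |

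Only the third row differs. Because of the fourth, stopping with a finding present is possible under both wordings. Because of the second, meeting the named circumstance is not enough to stop under either.

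**2. Is such a finding left without a rule?** No. A symptom present at baseline and still present at the last assessment does not meet the definition of resolution, so it counts as not resolved. In the time-to-event analysis, "if no events have occurred as of the day after the final IMP administration of the study drug", the subject is censored at that point. The rule is the same for all six findings.

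**3. Could the wording move a result?** The SAP gives no figure for this, so every input here is assumed:
- two baseline findings, each resolving by Day 15 in P = 60% (active) or 40% (placebo) if treatment continues;
- constant daily chance h = 1 − (1 − P)^(1/15), and no relapse;
- correlation between the findings of 0 to 0.6;
- a share q of subjects in whom one of the two findings clears on day d ≤ 13 is stopped, with the last assessment on day d + 1. All others are assessed on Day 15.

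The crude rate is linear in q: rate(q) = P − q × (P − rate at q = 1). With correlation 0, enumeration gives rates at q = 1 of 45.6% and 33.6%. For q = 0.25:
- active: 60 − 0.25 × (60 − 45.6) = 56.4%
- placebo: 40 − 0.25 × (40 − 33.6) = 38.4%
- difference: 18.0 points

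| q | Crude difference, correlation 0 to 0.6 | Kaplan-Meier Day 15 difference |
|---|---|---|
| 25% | 18.0 to 18.4 | 19.9 to 20.0 |
| 50% | 16.0 to 16.5 | 19.2 to 20.0 |
| 100% | 12.1 to 13.3 | 18.0 to 19.9 |

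At q = 5% to 10% the same formula gives a crude difference of 19.2 to 19.7 points, a loss of under 1 point.

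The comparison case under *all* (20 points at every q) holds only if the other-cases clause in Section 3.1 is ignored. The true gap between the two wordings is therefore no larger than the table suggests, and could be smaller.

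**4. Size against precision.** If all 31 subjects per group had the finding at baseline, which is the most favourable case, the 95% half-width for 60% versus 40% is 1.96 × √(0.6 × 0.4/31 + 0.4 × 0.6/31) = 1.96 × 0.124 = 0.244, or about 24 points. Losses of 1.6 to 4 points at q = 25% to 50% are small beside this.

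**5. Sample size.** The plan's 31 per group rests on a body-weight difference of 1.09 kg and an SD of 1.30 kg. A two-sample t-test at two-sided 5% and 90% power needs 30.9, rounded up to 31, with power 0.901. The stopping circumstance does not enter that calculation.

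**The case for a change.** The strongest case for a change is that the contradiction is real and early completion is built into the design. Section 7.1 counts early completers as having completed the trial, and Section 3.4 gives their end-of-treatment visit its own handling. The findings that prompt stopping are the endpoints themselves. A count, by group, of early completers with each finding still present would help a reader judge the crude rate. So would a Kaplan-Meier Day 15 estimate beside that rate and a sentence on informative censoring. The data are already listed (PDATA-1, EFF-2, EFF-3, EFF-6), so the cost is small.

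Much of this stands. The two sections do conflict. The crude rate does mix shortened and full courses, and censoring at early completion may be informative. But the mixing arises under either wording, because both allow other cases, so settling the wording would not remove it.

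The claim that the mixing is greater where the drug works better is an output of the assumed rates with equal q and equal correlation in both arms. It is not something the plan shows.

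The plan already reports 14-day and early completers separately (7.1). It also has shift tables to the last assessment, Kaplan-Meier tables for all six findings (CT-6.1.4, CT-6.2.2, CT-6.3.4) and subject listings. The additions would be reasonable reporting choices, but they do not correct an error.

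**Conclusion.** No change to the analyses follows. Sections 3.1 and 3.2 contain a wording conflict in a summary of trial conduct. The two passages must be reconciled with each other and with the protocol, and which wording applies is for the sponsor's clinical team. Either way, the definition of resolution, the censoring rule, the estimates and the tests stay as written.

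The claim that the plan does not say how a persisting finding is read does not hold.

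The possible attenuation is about 2 points at q = 25% and about 4 at q = 50%, out of 20. It applies to a secondary crude rate with a half-width of about 24 points. The planned Kaplan-Meier difference loses at most 0.8 points over that range. The larger loss at q = 100% requires every subject with one resolved finding to be stopped, although both sections also require the investigator's judgement. These sizes rest wholly on assumed inputs. No effect on the primary endpoint or on the sample size is shown.

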3.2 Trial Treatments

- Dosage regimen: Oral administration once daily

- Dose: OPC-131461 at 1 mg/day, 2 mg/day, 5 mg/day, 10 mg/day, or 0 mg
- Treatment duration: 14 days (However, the treatment will be terminated before completing 14 days of treatment, if the investigator or subinvestigator judges that no further improvement of volume overload is necessary in a case that any of congestive findings [lower limb edema, pulmonary congestion, jugular venous distension, hepatomegaly, pulmonary rales, and cardiac third sound] were resolved or in other cases.)

3.3 Trial Population

A total of 155 Japanese male and female subjects (31 subjects each in 5 groups; the target number of subjects who will begin the trial treatment) who are between the ages of 18 and 89 years, inclusive at the time of informed consent, and who are suffering from CHF with volume overload (lower limb edema, pulmonary congestion, or jugular venous distension) despite having received diuretics other than vasopressin receptor antagonists will be enrolled in the trial.

3.4 Handling of Time Points

Efficacy, safety, and exploratory endpoints will be described (see [Section 11.2](#) for baseline pharmacodynamic endpoints).

The analysis visit used for tabulating each visit will be the CRF visit and time point values. Follow-up examinations for pharmacokinetic endpoints and pharmacodynamic endpoints will not be tabulated. However, the completion/discontinuation test visits will be classified into the following analysis visits.

- End-of-treatment examination in subjects who completed 14-day IMP administration: Day 15
- End-of-treatment examination in early completers: Visit on the applicable day (excluding congestive findings, chest X-ray [cardiothoracic ratio, pulmonary congestion], NYHA classification, and 12-lead ECG [Because these items, which are specified to be measured at a feasible time after IMP administration, are measured after IMP administration during treatment, while for early completers, IMP will not be administered the next day.])
- Withdrawal Examination: Visit at discontinuation (not tabulated as visit of discontinuation)

Post-treatment observation will be classified as Day 16 for patients who have completed 14 days of IMP administration (however, post-treatment observation analysis visits will also be prepared for items other than PK and PD endpoints).

Echocardiography will be classified as “Day 15-16” if it is assessed at the completion/discontinuation test visit or post-treatment observation.

For pulmonary congestion, cardiothoracic ratio, and NYHA classification, if IMP is administered for less than 7 days, the day after IMP administration will be included in the analysis visit “Last assessment by Day 7 (day of IMP administration).”

The baseline of each item is defined as follows.

Table 3.4-1 **Handling of Time Points**

*If there are multiple data in the run-in period, the data closest to Day 1 will be adopted as the baseline.

4 Sample Size

The sample size is set as 31 subjects per group.

Assuming that a dose of OPC-131461 at 5 mg or higher is equivalent to 15 mg of tolvaptan in patients with CHF, the sample size required to demonstrate the superiority of OPC-131461 over placebo in terms of the primary endpoint, ie, the change in body weight from baseline to the last assessment time point (the day after IMP administration) by Day 8, was determined (multiplicity relating to the use of more than one OPC-131461 dose group was not considered).

The results of the phase 3 confirmatory trial of tolvaptan (Protocol 156-06-002; placebo-controlled 7-day treatment) demonstrated that the change from baseline in body weight on the day after the final IMP administration (LOCF) was -0.45 ± 0.93 kg (mean \pm standard deviation [hereinafter, the same applies]) for the placebo group and -1.54 ± 1.61 kg for the tolvaptan 15-mg group. Based on these results, assuming a treatment difference of -1.09 , standard deviation (combined) of 1.30 , statistical power of 90% , and two-sided significance level of 5% , the sample size required is set as 31 subjects per group for a total of 155 subjects.

5 Statistical Analysis Datasets

